# Clinical Study Protocol

## Johnson & Johnson Vision Care, Inc.

### **CLUE Scores:**

The CLUE comfort scores will be analyzed using a linear mixed model to assess the difference between the Test (AO1D) and Control (subjects' habitual lens). The regression model will include lens type and baseline score as fixed effect factors. Baseline characteristics such as age and gender may also be included as fixed effect covariates in the model when appropriate. Investigational site will be included as a random effect. The correlation measurements from the same subjects across lens type will be modeled using UN variance-covariance matrix. If the estimation algorithm does not converge, then a CS or CSH covariance matrix will be used. The Kenward and Roger method will be used to calculate the denominator degree of freedom.

### **Hypothesis Testing:**

The null and alternative hypotheses for non-inferiority of the Test relative to Control are as follows:

$$H_0: \Delta \leq -5$$

$$H_A: \Delta > -5,$$

where  $\Delta$  is the difference between lens types at 2-week follow-up (Test minus Control). Non-inferiority of the Test lens relative to the Control lens will be tested using 2-sided 95% CIs constructed for the LSM difference at 2-week follow-up from the final model. Non-inferiority of the Test relative to the Control (Subjects' habitual lens) will be established if the lower bound of the 95% CI is greater than -5. If non-inferiority of the Test lens over Control lens is met, then superiority test will be also conducted on the ITT population. If the lower bound is greater than 0, then the superiority of the Test lens over the Control lens will be established.

### **14.7. Other Exploratory Analysis**

The following other study endpoints will be assessed in support of primary and secondary endpoints. Exploratory Endpoints will only be tested and analyzed if all primary and secondary hypotheses are met.

#### **1. CLDEQ Questions:**

- During a typical day in the past 2 weeks, how often did your eyes feel discomfort while wearing your contact lenses?
- When your eyes felt discomfort with your contact lenses, how intense was this feeling of discomfort (on a scale of 1-5) at the end of your wearing time?
- During a typical day in the past 2 weeks, how often did your eyes feel dry?
- When your eyes felt dry, how intense was this feeling of dryness (on a scale of 1-5) at the end of your wearing time?

#### **2. CLUE Comfort Questions:**

- These contact lenses were very comfortable (C001\_2)
- I could wear these contact lenses comfortably for as long as I wanted to (C008\_1)
- These lenses were very comfortable at the end of the day (C020\_2)
- My eyes felt very dry at the end of the day (C021\_2)

# **Clinical Study Protocol**

## **Johnson & Johnson Vision Care, Inc.**

- My eyes felt dry all day (C022\_1)
- My eyes felt dry at the end of the day (C023\_1)
- I have experienced dry eyes (C041\_1)
- The comfort of these lenses decreased throughout the day (C061\_1)

### 3. CLUE Vision Questions:

- I had very good vision at the end of the day (V004\_2)
- I experienced fluctuations in the quality of my vision (V009\_1)
- I was very satisfied with the quality of my vision in dim lighting (V013\_2)
- I was satisfied with the quality of my vision at night (V014\_1)
- I was very satisfied with the clarity of distant objects (V034\_2)
- I was satisfied with the clarity of near objects (V035\_1)
- I was very satisfied by the clarity of my vision at the end of the day (V037\_2)
- My vision with these lenses was exceptional (V124\_3)

### 4. MRD Questions:

- These lenses help to reduce the feeling of dryness at the end of the day (MIS01977)
  - Have you been able to use these lenses for 8 hours or more with digital devices? (MIS01978)
  - I would recommend them to people who experience dryness with their own contact lenses (P3\_0021\_p10)
- 
- Not making your eyes feel dry throughout the day (P3\_0006\_p38)
  - Keeping your eyes from feeling dry at the end of the day (P3\_0006\_p39)
  - Burning (P3\_0023\_p01)
  - Dryness (P3\_0023\_p02)
  - Grittiness (P3\_0023\_p03)

### 5. Preference Questions:

- Based on your overall opinion of both study lenses, do you prefer one lens more than the other? (PVC015\_1)
- Overall Comfort (PREF10\_3)
- Comfort at the end of the day (PREF10\_5)
- Overall vision (PREF10\_7)
- Keeping your eyes from feeling dry (PREF10\_14)

Tertiary hypotheses will be evaluated in the following manner.

1. If the primary hypothesis is not met, then the tertiary hypotheses will not be evaluated.
2. If the primary and secondary hypotheses are met: All tertiary hypotheses will be evaluated for both between the study arms and within the second arm.

# **Clinical Study Protocol**

## **Johnson & Johnson Vision Care, Inc.**

- a. If the primary and secondary hypotheses regarding CLUE comfort are met then the tertiary hypotheses relevant to this endpoint will be evaluated for both between the study arms and within the second arm.
- b. If only the primary hypothesis for CLUE comfort is met then, then associated tertiary hypotheses relevant to this endpoint will only be evaluated between study arms.
- c. If both secondary hypotheses regarding CLDEQ8-Scores are met, then the tertiary hypotheses relevant to this endpoint will be evaluated for between the study arms only and within the second arm.
- d. If only 1 of the secondary hypotheses regarding CLDEQ8-scores is met, then the associated tertiary hypotheses relevant to this endpoint will be evaluated between study arms.

### CLUE, MRD and CLDEQ-8 Individual Questions

Each of individual questions (not including preference questions) will be analyzed using a generalized linear mixed model for ordinal data with a multinomial distribution and cumulative logit function as a link function. The model will include lens type as a fixed effect factor and site as a random effect factor. The assumption of proportionality of odds ratio across response categories will be assessed graphically. If this assumption is violated, then the distribution of response will be investigated. If sparse data is observed, then the spare responses may be collapsed to ensure that each response category has sufficient data for the analysis. If the assumption of proportionality of odds is still violated in the collapsed categories, then a partial proportional odds model may be considered. A generalized estimation equation (GEE) may also be considered if necessary. Comparison between the Test and Control lenses at 2-week follow-up will be carried out using 2-sided 95% CI of odds ratio (OR, Test over Control) where the odds ratio represents the odds of having a higher positive rating/experience for the Test lens compared to the Control lens. Non-inferiority will be conducted on the Per-Protocol population. Non-inferiority will be tested by comparing the lower limit of the 95% confidence interval for the odds ratio (Test over Control) to 0.67. If the lower limit is above 0.67 non-inferiority of the Test lens relative to the Control lens will be established. If non-inferiority is met then Superiority will be tested on the ITT population by comparing the lower limit of the 95% CI to 1. The Test lens will be concluded to be superior to the Control lens if the lower limit of the CI is above 1.

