**Clinical Study Protocol**  
**Johnson & Johnson Vision Care, Inc.**

| ARM 2  |                                |  |
|---|--------------------------------|--|
| Visit 2: Treatment 1, 2-Week Follow-Up; Treatment 2 Fitting |                                |  |
| Step  | Procedure                      | Details  |
| 2.5.  | CLDEQ-8 Questionnaire          | 
The subject will respond to the CLDEQ-8 Questionnaire (Appendix A).
 
NOTE: If subjects no longer meet score criteria of <math>\geq 15</math>, the lenses will be removed by the subject and discarded. The subject will be discontinued and proceed to final evaluation (F.1)
   |
| 2.6.  | Follow Up questionnaires       | 
The subject will respond to the CLUE and MRD Follow Up Questionnaire (Appendix A)
   |
| 2.7.  | Entrance Visual Acuity         | 
Record the distance Snellen visual acuity with the contact lenses (OD, OS) to the nearest letter. Subjects must read the smallest line until at least 50% of the letters are read incorrectly.
  |
| 2.8.  | Subjective Lens Fit Assessment | 
Evaluate overall lens fit acceptance (acceptable or unacceptable) based on centration, movement and other fitting characteristics.
 
An unacceptable fit is deemed by one of the following criteria:
 
 
• limbal exposure at primary gaze or with extreme eye movement.
 
• edge lift.
 
• excessive movement in primary and up gaze.
 
• insufficient movement in all three of the following conditions: primary gaze, up gaze, and Josephson push up.
 
 
NOTE: if lens fit is unacceptable subject will be discontinued from the study.
 |
| 2.9.  | Lens Removal and Discard       | 
The lenses will be removed by the subject and discarded.
  |

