### **14.4. Level of Statistical Significance**

All planned analysis for this study will be conducted with an overall type I error rate of 5%. The study hypotheses will be tested using the following gatekeeping strategy; If the primary hypothesis is met, then the secondary hypotheses will be tested. If the primary and secondary hypotheses are met, all tertiary hypotheses will be evaluated for both between the study arms and within the second arm. If the primary and secondary hypotheses regarding CLUE comfort are met, then the tertiary hypotheses relevant to this endpoint will be evaluated for both between the study arms and within the second arm. If only the primary hypothesis for CLUE comfort is met then, then associated tertiary hypotheses relevant to this endpoint will only be evaluated between study arms. If both secondary hypotheses regarding CLDEQ8-Scores are met, then the tertiary hypotheses relevant to this endpoint will be evaluated for between the study arms only and within the second arm. If only 1 of the secondary hypotheses regarding CLDEQ8-scores is met, then the associated tertiary hypotheses relevant to this endpoint will be evaluated between study arms.

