### **CLDEQ-8 Total Scores:**

The CLDEQ-8 total scores will be analyzed using a linear mixed model to assess the difference between the Test and Control (subjects' habitual lens) lenses within ARM 2. The regression model will include lens type (Habitual lens and AO1D), and baseline score as fixed effect factors. Baseline characteristics such as age and gender may be included as fixed effect covariates in the model when appropriate Investigational site will be included as a random effect.. The correlation measurements from the same subjects across lens type (Habitual and AO1D) will be model using Unstructured (UN) variance-covariance matrix. If the estimation algorithm does not converge, then a Compound Symmetry (CS) or heterogenous compound symmetric (CSH) matrix will be used. The Kenward and Roger method will be used to calculate the denominator degree of freedom.

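### Section 14.7 item model has no term for paired lens ratings when it is used within ARM 2, so its 95% limits are the wrong width, probably by a little (minor)

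*Combined protocol and SAP*

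**What the plan says.** Section 14.7 (CLUE, MRD and CLDEQ-8 Individual Questions) sets one ordinal model for 4 CLDEQ-8, 8 CLUE comfort, 8 CLUE vision and 8 MRD items: "The model will include lens type as a fixed effect factor and site as a random effect factor". After the text on proportional odds and sparse categories it adds: "A generalized estimation equation (GEE) may also be considered if necessary". The lower 95% limit of the odds ratio is compared with 0.67 for non-inferiority on the per-protocol set, and then: "If non-inferiority is met then Superiority will be tested on the ITT population by comparing the lower limit of the 95% CI to 1".

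The model serves two comparisons. If the primary and secondary hypotheses are met, 14.7 states: "All tertiary hypotheses will be evaluated for both between the study arms and within the second arm". Sections 2.3 and 14.4 say the same. In ARM 2 each subject answers the items for the habitual lens at Visit 2 and for AO1D at Visit 3.

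For the within-ARM 2 total scores, Section 14.6 does provide for the pairing. For CLDEQ-8: "The correlation measurements from the same subjects across lens type (Habitual and AO1D) will be model using Unstructured (UN) variance-covariance matrix". For CLUE comfort: "The correlation measurements from the same subjects across lens type will be modeled using UN variance-covariance matrix".

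**The concern.** Within ARM 2 the two ratings being compared come from the same person. A model with only lens type and site treats them as independent once site is accounted for. Its standard error for the lens effect is then wrong at any non-zero within-subject correlation: too large if the correlation is positive, too small if negative. The 95% limits carry the decision directly, so the error bears on which item-level statements can be made in a study meant to support marketing claims (Section 2.1). The plan handles the same pairing explicitly for the total scores, so this is an inconsistency within the plan and not a matter of taste in modelling.

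**Working it through.** **1. The plan's own figures.** The documents state no power, standard error or correlation for the item model. Table 9's 40 per arm concerns the change in CLUE comfort. It reproduces exactly with a Satterthwaite t-test, SDs 25.21 and 18.12, distance 9 + 5 = 14, two-sided alpha 0.05 and 80% power. Here it supplies only the number of pairs: 40 ARM 2 completers.

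**2. Proxy correlations (Section 14.2, Overall rows, n=24).** r = (s1² + s2² − s_diff²) / (2·s1·s2).

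- CLUE comfort, Table 8: (18.78² + 18.12² − 25.21²) / (2 × 18.78 × 18.12) = 45.48 / 680.59 = 0.067.
- CLDEQ-8, Table 7: (6.35² + 4.39² − 7.17²) / (2 × 6.35 × 4.39) = 8.19 / 55.75 = 0.147.

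Fisher 95% intervals, tanh(atanh r ± 1.96/√21), are −0.35 to 0.46 and −0.27 to 0.52. Both include zero. The by-study rows give values from −0.59 (n=5) to 0.49 (n=8). These are total scores, and the habitual score was taken at baseline, so they only stand in for the item correlations between Visit 2 and Visit 3.

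**3. Score-level effect of ignoring the pairing.** Ratio = √(s1² + s2²) / s_diff.

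- CLUE: 26.10 / 25.21 = 1.035.
- CLDEQ-8: 7.72 / 7.17 = 1.077.

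**4. Item-level effect.** For an independence cumulative-logit fit to n pairs, the model-based variance is A⁻¹/n. The variance that respects the pairing is A⁻¹MA⁻¹/n, with M = A + C + Cᵀ. A is the summed information of the two ratings and C the cross-product of their scores. Inputs are assumed: Gaussian-copula pairs, four five-category and two binary response distributions, true odds ratio 1 or 2, no site term.

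For categories 0.10/0.20/0.40/0.20/0.10, odds ratio 1 and 40 pairs, the model SE is 0.404. The table's last column is the point estimate needed for the lower limit to reach 0.67, that is 0.67·exp(1.96·SE). As written it is 0.67·exp(1.96 × 0.404) = 1.48.

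| Latent correlation | Paired SE | Model SE too wide by | Estimate needed, paired |
|---|---|---|---|
| 0.067 | 0.392 | 3.1% | 1.44 |
| 0.147 | 0.377 | 7.3% | 1.40 |
| 0.3 (assumed) | 0.346 | 16.9% | 1.32 |
| 0.5 (assumed) | 0.300 | 34.8% | 1.21 |

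Across all the distributions:

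| Latent correlation | Five-category items | Binary items |
|---|---|---|
| 0.067 | 2.6-3.1% | 1.5-2.2% |
| 0.147 | 6-7% | 3.4-5.1% |
| 0.3 (assumed) | 14-17% | 8-11% |
| 0.5 (assumed) | 27-35% | 16-23% |

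**5. Consequence for decisions.** For the symmetric item with 40 pairs, false non-inferiority at a true odds ratio of 0.67 (nominal 2.5%) falls to about 2.2%, 1.8%, 1.1% and 0.4-0.5% at the four correlations. Power was simulated at odds ratio 1.5 with 40 complete pairs, no site term, and small-sample-corrected clustered standard errors on 39 df. As written against clustered it is 53% vs 51% (0.07), 53% vs 54% (0.15), 52% vs 62% (0.3) and 52% vs 74% (0.5).

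**The case against.** **The effect is negligible on the evidence available.** Largely right. At the two proxy values the power difference is within about two points either way. The proxies are weak, and the larger effects rest on assumed correlations. All the percentages above also leave out site. No run used the plan's random site effect. With site entered as fixed dummies in both fits (3, 5 or 8 sites assumed), the ratio of model to clustered SE is 0.92-1.03 at 0.07-0.15, so that form of correction can cost precision. This stands, and it limits both the severity and the fix.

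**The GEE sentence already covers it.** It does not. It is optional, follows the proportional-odds text, and names no trigger, cluster or working correlation.

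**Section 14.1 defers detail to a stand-alone SAP.** True, and the point can be settled there. But Section 14.10 commits the analysis to what the protocol specifies, and what it specifies omits the pairing.

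**A reader might infer inflated false claims.** The documents do not support that. Both Overall-row correlations are positive, and then the error is conservative. A negative correlation, which would make the limits too narrow, cannot be excluded from n=24, but nothing shows it. A reader might equally infer a large loss of power; that holds only at the assumed 0.3-0.5.

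**Selection matters more.** Step 2.5 at ARM 2 Visit 2 says of subjects whose CLDEQ-8 falls below 15: "The subject will be discontinued and proceed to final evaluation (F.1". That is a separate matter. It neither creates the pairing problem nor is cured by modelling the pairing.

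**Conclusion.** The point holds as a minor one. As written, the item model gives within-ARM 2 intervals of the wrong width at any non-zero within-subject correlation, while the Section 14.6 models do not. On the only figures in the documents, item standard errors are about 1.5-7% too wide before any site term, with little or no power to gain. At assumed latent correlations of 0.3-0.5 the excess is about 14-35% for five-category items and less for binary ones.

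The structural finding rests on the text alone. The size rests on total-score proxies from 24 subjects, on assumed response distributions (Appendix A is not shown), and on 40 complete, unselected pairs.

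Only tertiary claims that depend on earlier hypotheses are touched. The opening of 14.7 and the list of conditions later in that section differ on how much must be met first, but within-ARM 2 item tests are planned under either. The primary and secondary analyses are unaffected. So are the between-arm item comparisons, which use one 2-week rating per subject if, as for the primary endpoint, only the first ARM 2 period enters.

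**What to change.** Keep the stated model for between-arm items. For within-ARM 2 items, replace the optional GEE sentence, in 14.7 or in the stand-alone SAP before database lock, with wording such as:

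*For within-ARM 2 item comparisons, a cumulative-logit GEE clustered on subject with small-sample-corrected robust standard errors will be used; the 0.67 and 1 thresholds apply to the marginal odds ratio.*

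Do not require site as a fixed factor in this fit. With complete pairs, each site contributes equal numbers of ratings for the two lenses, so leaving site out does not confound the comparison.

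The cost is one sentence, with no new data or subjects. There are two downsides: slightly less precision if the correlation is near zero, and loss of some conservatism if it is positive. The change does not address selection of ARM 2 subjects at step 2.5.

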### Preference Questions

The item responses will be analyzed using a generalized linear mixed model with a multinomial distribution and the generalized logit as the link function. The analysis model may include lens type and other subject characteristics such as gender as fixed covariates when appropriate. Site will be included as a random effect (G-side).

Comparisons between the Test and Control will be constructed using two-sided 95% confidence intervals for the preference ratio (the proportion of subjects preferring the Test lens compared to the Control lens – Test over Control). Superiority will be conducted on the ITT population by comparing the lower limit of the 95% CI to 1. The Test lens will be concluded to be superior to the Control lens if the lower limit of the CI is above 1.

# **Clinical Study Protocol**

## **Johnson & Johnson Vision Care, Inc.**

### **14.8. Interim Analysis**

No Interim analysis will be performed on this study.

### **14.9. Procedure for Handling Missing Data and Drop-Outs**

Missing or spurious values will not be imputed. The count of missing values will be included in the summary tables and listings.

Subject dropout is expected to be one of the main reasons of missing data in this clinical trial. Past clinical trials don't provide the evidence that subject dropout is systematic or not-at-random. To evaluate the impact of missing data, sensitivity analysis will be conducted using multiple imputation methods if the proportion of subject dropout is greater than the 15%. The SAS/STAT procedures PROC MI and PROC MIANALYZE will be utilized with a parametric regression method used to make at least 20 imputations.

### **14.10. Procedure for Reporting Deviations from Statistical Plan**

The analysis will be conducted according to that specified in above sections. There are no known reasons for which it is planned to deviate from these analysis methods. If for any reason a change is made, the change will be documented in the study report along with a justification for the change.

## **15. DATA HANDLING AND RECORD KEEPING/ARCHIVING**

### **15.1. Electronic Case Report Form/Data Collection**

The data for this study will be captured on electronic case report forms (eCRFs) using the BioClinica EDC system. An authorized data originator will enter study data into the eCRFs using the EDC system. Data collected on equipment that is not captured in EDC will be formatted to the specification of the JJVC database manager and sent to JJVC for analysis.

External data sources for this study include: Not Applicable

The clinical data will be recorded on dedicated eCRFs specifically designed to match the study procedures for each visit. Only specifically delegated staff can enter data on a CRF. Once completed, the eCRFs will be reviewed for accuracy and completeness and signed by the Investigator. The sponsor or sponsor's representatives will be authorized to gain access to the subject recordation for the purposes of monitoring and auditing the study.

Edit checks, electronic queries, and audit trails are built into the system to ensure accurate and complete data collection. Data will be transmitted from the clinical site to a secure central database as forms are completed or updated, ensuring information accuracy, security, and confidentiality. After the final database lock, the Investigator will be provided with Individual Patient Profiles (IPP) including the full audit trail on electronic media in PDF format for all of the study data. The IPP must be retained in the study files as a certified copy of the source data for the study.

# **Clinical Study Protocol**

## **Johnson & Johnson Vision Care, Inc.**

The content and structure of the eCRFs are compliant with ISO14155:2011.

### **15.2. Subject Record**

At a minimum, subject record should be available for the following:

- subject identification
- eligibility
- study identification
- study discussion
- provision of and date of informed consent
- visit dates
- results of safety and efficacy parameters as required by the protocol
- a record of all adverse events
- follow-up of adverse events
- medical history and concomitant medication
- test article receipt/dispensing/return records
- date of study completion
- reason for early discontinuation of test article or withdrawal from the study, if applicable

The subject record is the eCRF or an external record. The author of an entry in the subject record must be identifiable. The first point of entry is considered to be the source record.

Adverse event notes must be reviewed and initialed by the Investigator.

